If the patient does not have the capacity to give written informed consent due to his/her current health state, the surrogate will provide written informed consent prior to the patient's enrollment in the study. The patient will be re-evaluated periodically for the capacity to give consent. The SC will confirm with the treating hepatologist if the patient is capable of providing written informed consent while inpatient. If the patient is found capable, the study coordinator will obtain written informed consent from the patient. If the patient is found to be capable, but is discharged prior to providing written informed consent, the study coordinator will contact the patient by telephone. The patient will sign the e-consent form in a similar manner as the surrogate decision-maker e-consent procedures described above. If the patient does not have access to a computer, and the patient provides verbal permission, a paper informed consent form for the patient to sign and return, a blank copy for the patient to keep, and a stamped addressed envelope to return the signed copy will be mailed to the patient. If the patient is found capable and declines participation, the patient and surrogate will be immediately terminated from the study. Study staff will print a copy of the signed document, and give to participant at time of study visit. Should a participant choose to receive a link to the consent document in lieu of a hard copy (or if they sign electronically from a remote location), they will receive a link to a ROCKET site containing the consent form appropriate to the version date that they signed. Signed consent documents will NOT be housed electronically on ROCKET. No research procedures will be performed until after consent has been provided.

After written informed consent is provided by the patient or surrogate, baseline measures will be completed, and patients will then be randomized (stratified by treating hepatologist) to the control or intervention arm using validated computer programs (**see Figure 3**). If the surrogate decision-maker provided consent for

the patient, patients will be randomized, but baseline measures will be completed by the patient after providing written informed consent. A panel within the EMR containing all enrolled patients and the arm assignment will be created and shared with the PC team.

[figure not shown]

Figure 3. Approach for Study Participant Selection

Caregiver Participation

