6.0 Intervention

We will conduct a randomized, controlled study to evaluate the impact of systematic, comprehensive palliative care services vs. usual hepatic care. After providing written informed consent, patients will complete baseline measures including demographic (**Appendix C**), mood, and quality of life questionnaires on the inpatient unit. Patients will be randomized to either the control (usual hepatic care) or the intervention arm (usual hepatic care with comprehensive palliative care services). Patients who are randomly assigned to usual care will not be scheduled to meet with the palliative care service unless a meeting is requested by the patient, the family, or the treating physician.

Patients randomized to the intervention arm will receive a binder (**Appendix D**) of patient materials including general information about palliative care services, the COMPASS study, and templates to document information if the patient wishes (names of medicine, upcoming appointments, important contact information, etc.). Intervention patients will also receive , contact information printed on a magnet (**Appendix F**), a wallet card (**Appendix G**), and a one-page handout (**Appendix H**). A VUMC palliative care physician or nurse practitioner will meet with the patient and appropriate surrogate, caregiver, family members, etc. after randomization to provide a verbal overview detailing palliative care services and to provide the comprehensive initial consult. Appropriate palliative care providers will provide follow-up in-person consults while the patient remains inpatient per usual palliative care services.

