7.0 Data collection

7.1 Primary Outcome Data

Primary outcome data (hospital admission and discharge dates) will be obtained for this study through retrospective chart review utilizing StarPanel and the Research Derivative (RD). The RD is a database of clinical and related data derived from the Medical Center's clinical systems and restructured for research. Data is repurposed from VU's enterprise data warehouse, which includes data from StarPanel, VPIMS, and

ORMIS (Operating Room Management Information System), EPIC, Medipac, and HEO among others. The medical record number and other person identifiers are preserved within the database. Data types include reimbursement codes, clinical notes and documentation, nursing records, medication data, laboratory data, encounter and visit data, among others. Output may include structured data points, such as ICD 9 codes or encounter dates, semi-structured data such as laboratory tests and results, or unstructured data such as physician progress reports. The database is maintained by the Office of Research Informatics under the direction of [name].

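### Patients randomised on surrogate consent who later decline are ended from the study, and neither the consent procedures nor the analysis plan provides for chart follow-up or says how they are analysed

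*Combined protocol and SAP*

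**What the plan says.** Under Consent Procedures in Section 5.0, when a patient lacks capacity, "the surrogate will provide written informed consent prior to the patient's enrollment in the study". In that case "patients will be randomized, but baseline measures will be completed by the patient after providing written informed consent", so allocation comes before the patient's own decision. Capacity is reassessed periodically, and the patient's decision may come after the hospital stay, since the coordinator phones a patient who has gone home without signing. For a capable patient who refuses, the rule is: "the patient and surrogate will be immediately terminated from the study".

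The arm is not concealed. Section 5.0 states: "A panel within the EMR containing all enrolled patients and the arm assignment will be created and shared with the PC team". Section 6.0 adds: "Patients randomized to the intervention arm will receive a binder", together with other printed materials and a meeting with a palliative care clinician after randomisation.

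Section 7.1 says: "Primary outcome data (hospital admission and discharge dates) will be obtained for this study through retrospective chart review", supplemented by the institution's research database. Section 7.2 draws hospitalisations, hospice use, days alive outside hospital, date of death, symptoms and transplant status from the same sources. Section 8.0 (Statistical Analyses) compares outcomes by assigned arm. It defines no analysis set, makes no intention-to-treat statement and gives no rule for withdrawals.

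**The concern.** A patient who regains capacity is asked to decide after allocation. An intervention patient may by then have met the palliative care team and received its materials; a control patient will not have done so through the study. The protocol itself describes widespread misunderstanding of palliative care (Section 1.0) and the worry that patients may think their clinicians are giving up (Section 3.0). Refusal could therefore differ between arms. If it did, and if refusers also differed in readmission risk, losing their outcomes would disturb the randomised comparison.

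Much of this loss may be avoidable. The primary outcome is a readmission date in the medical record and needs no visit, call or questionnaire. A patient who wants no further contact might still allow the record to be read, but Section 5.0 describes only termination.

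**Working it through.** **1. Order of events.** Surrogate consent, randomisation, arm visible to the team and possibly the patient, capacity regained, refusal, termination. Section 5.0 bars research procedures before consent, but it lets randomisation follow consent by patient or surrogate. Section 6.0 does not hold the palliative care consult until the patient has personally agreed. Refusal can therefore come after the intervention has started.

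**2. The plan's own figure.** Table 3 gives minimum detectable hazard ratios for N = 400, power 80% and type I error 0.05 (sidedness not stated; two-sided reproduces the table). With events D = 400 × R, where R is control-arm readmission risk, and a = (1.960 + 0.842)/√D, the Freedman form is HR = (1 − a)/(1 + a). For R = 60%: D = 240, a = 2.802/15.49 = 0.181, HR = 0.819/1.181 = 0.694.

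| R | Stated HR | Reproduced HR |
|---|---|---|
| 50% | 0.67 | 0.669 |
| 60% | 0.69 | 0.694 |
| 70% | 0.71 | 0.713 |
| 80% | 0.73 | 0.729 |
| 90% | 0.74 | 0.743 |

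All five rows match, and nothing here disputes them. No allowance for withdrawals is stated.

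**3. How many patients.** The documents give neither share. Assuming 10–40% enrol by surrogate and 10–30% of those decline:

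- low: 400 × 0.10 × 0.10 = 4
- high: 400 × 0.40 × 0.30 = 48

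That is 1% to 12% of those randomised.

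**4. Power if a share d is excluded.** Schoenfeld form: power = Φ(½√D × |ln HR| − 1.960), with D = 400(1 − d)R and the stated HRs. For R = 60%, HR = 0.69 and d = 10%: D = 216, ½√216 × 0.371 = 2.727, and Φ(0.767) = 0.778.

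| d | Power, R = 60% | Range over the five rows |
|---|---|---|
| 0% | 0.820 | 0.804–0.820 |
| 2% | 0.812 | 0.796–0.812 |
| 5% | 0.800 | 0.783–0.800 |
| 10% | 0.778 | 0.761–0.778 |

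The loss is about 4 points at 10%. Censoring at termination would cost less, because readmissions before that date still count.

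**5. Bias if exclusion differs by arm.** Assume no true effect, overall readmission risk 0.60 in both arms, and risk q in those removed. The risk in those who remain is r = (0.60 − d·q)/(1 − d), and the apparent HR is ln(1 − r_int)/ln(1 − r_con). Take 2% of controls and 10% of intervention patients removed (4 and 20 of 200):

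- q = 0.80: r_con = 0.584/0.98 = 0.596; r_int = 0.520/0.90 = 0.578; HR = 0.952
- q = 0.40: r_con = 0.592/0.98 = 0.604; r_int = 0.560/0.90 = 0.622; HR = 1.051

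With 5% against 10%, the values are 0.968 and 1.032. With equal removal in both arms, or q = 0.60, the HR stays at 1.000.

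**The case against.** Several stronger readings are tempting, and the documents do not carry them.

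- **These patients are dropped from the analysis.** Section 5.0 ends their participation. It does not say that their data are deleted or that they leave the comparison; censoring at termination fits the words equally well. Step 5 therefore illustrates one reading.
- **The plan offers no lesser exit.** This can be said only of Section 5.0 and Section 8.0. The consent forms were not available for this review and may address data after withdrawal.
- **The sickest patients are lost.** The rule touches only patients found capable. Those who stay incapacitated, or die first, are not removed by it. Nothing shows that decliners have a worse prognosis than other participants.
- **Refusal is linked to treatment.** It could be, but this is not shown. Section 6.0 notes that most of the services are available to all patients in routine care, which weakens the mechanism without excluding it.

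The ethical objection has real force. A decliner never personally consented, and the availability of a chart does not authorise its use. Full withdrawal must remain open. It is also fair that Section 8.0 is silent on withdrawals of every kind, while Section 5.0 lets any participant leave at any time; this is one instance of that gap.

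What stands is narrower. The stated rule gives up one-year primary data that some decliners might willingly allow, and the analysis plan does not say what follows.

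**Conclusion.** The concern holds in limited form. Ending participation after randomisation loses primary outcome data in patients who regain capacity and decline, at a point when the arm may be known to them. Exclusion or censoring would both leave this loss, and neither is specified.

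The effect is probably modest. The count of 4 to 48 rests on assumed shares. Moving a null hazard ratio by about 0.05 in either direction took a five-fold difference in removal between arms together with a 20-point difference in risk, all assumed. The documents do not fix the direction. This is a cheap improvement rather than a serious flaw, and confidence in its size is low.

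**What to change.** In Section 5.0, unless the consent form already does so, replace immediate full termination with a documented choice:

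- (a) stop study contacts and questionnaires but permit chart review to one year; or
- (b) withdraw fully.

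In Section 8.0 (Statistical Analyses):

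- State that all randomised patients are analysed as assigned, as far as consent allows. Follow group (a) to one year, and censor group (b) at withdrawal if data to that date may be kept.
- Report declines by arm and by time since randomisation.
- Add a sensitivity analysis for group (b). Censoring alone does not remove the problem, because it may be informative.

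The cost is one added consent option, ethics review of its wording and a short addition to the analysis plan. Patients who refuse chart review are still lost.

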6.0 Intervention

We will conduct a randomized, controlled study to evaluate the impact of systematic, comprehensive palliative care services vs. usual hepatic care. After providing written informed consent, patients will complete baseline measures including demographic (**Appendix C**), mood, and quality of life questionnaires on the inpatient unit. Patients will be randomized to either the control (usual hepatic care) or the intervention arm (usual hepatic care with comprehensive palliative care services). Patients who are randomly assigned to usual care will not be scheduled to meet with the palliative care service unless a meeting is requested by the patient, the family, or the treating physician.

Patients randomized to the intervention arm will receive a binder (**Appendix D**) of patient materials including general information about palliative care services, the COMPASS study, and templates to document information if the patient wishes (names of medicine, upcoming appointments, important contact information, etc.). Intervention patients will also receive , contact information printed on a magnet (**Appendix F**), a wallet card (**Appendix G**), and a one-page handout (**Appendix H**). A VUMC palliative care physician or nurse practitioner will meet with the patient and appropriate surrogate, caregiver, family members, etc. after randomization to provide a verbal overview detailing palliative care services and to provide the comprehensive initial consult. Appropriate palliative care providers will provide follow-up in-person consults while the patient remains inpatient per usual palliative care services.

If the patient is discharged, follow-up consults will be provided by a palliative care nurse via telephone contact with the patient and/or surrogate, caregiver, or other individuals involved in the patient's care as appropriate. The nurse will assess the patient's physical and mental functioning, review medications and discharge instructions, review the patient's advance care plan and goals of care, respond to patient questions, and identify needs for additional care (procedures outlined in Table 1). The nurse will be provided a semi-structured telephone guide, informed in part by the Re-Engineered Discharge (RED) toolkit supported by Agency for Healthcare Research and Quality²⁸ (**Appendix I**). The initial telephone contact attempt will occur within 96 hours post-discharge. If initial call attempts are unsuccessful, the nurse will continue to contact the patient or other appropriate individuals up to 7 days post-discharge. If the patient and/or surrogate, caregiver, or other individual involved in the patient's care provides verbal permission for the team to send reminder texts or emails regarding the phone consults, and the nurse is unable to reach the individual by phone, the nurse may send text messages or emails. The text or email sent by the nurse will only serve to set up a time to complete the phone call. The nurse will not send sensitive health information via text or email. If unsuccessful after 7 days, the nurse will attempt contact again in 3 weeks (1 month after the scheduled contact). After the initial successful contact, telephone consultations will occur on a flexible schedule (e.g., weekly, bi-weekly, monthly) based on the needs and wishes of the patient, at a minimum frequency of once a month. Both the in-person inpatient consultations and the follow-up telephone contacts will be recorded using standard template forms via Starform in the patient's EMR (**Appendices J, K**).

During the telephone contact, if a palliative care nurse identifies a need for further care (e.g., referral to hospice, appointment with the outpatient palliative care office, appointment for symptom management, etc.), the nurse will engage the palliative care team and/or the Hepatology team as indicated. Nurses will relay all relevant information from the telephone contacts to the palliative care team and the treating hepatologists via StarPanel and other clinically appropriate communication channels. If the patient is readmitted to the hospital, the inpatient in-person follow-up and outpatient telephone follow-up schedule will restart. Patients will receive inpatient consultations and follow-up outpatient telephone consultations for one year after randomization to the intervention arm or until death.

After completion of the one-year intervention phase, patient participation will be complete. With the exception of the follow-up telephone contacts and patient-friendly materials, similar services are available to all patients per routine practices. There are no other investigational agents or processes being used for the intervention group of patients/providers. See **Figure 4** below for trial design.

[figure not shown]

Figure 4. RCT Study Schema

The palliative care intervention is expected to include:

- Informational, patient friendly Palliative Care Binder, magnet, handout, wallet card
- Establishment of a palliative care plan
- Care coordination by palliative care team
- Early and regular ongoing engagement of palliative care physicians and nurse practitioners for inpatient consultations
- Telephone contacts conducted by trained palliative care nurses to review palliative care plan, assess changes in symptoms, identify patient needs and re-engage the palliative care team or Hepatology team as appropriate for referrals or appointments
- Communication by palliative care team to all providers and teams involved in patient's care
- Systematic collection of information, including identification of surrogate or health care proxy and advance care planning

Inpatient and telephone palliative care consults will consist of a systematic process utilizing standardized template forms and will include all of the components outlined in **Table 1**.

Table 1

Palliative Care Intervention Procedures	Inpatient In-Person Consults	Outpatient Telephone Consults
Introduction to PC	X	
Introduction to concepts of Advance Directive, living will, healthcare agent	X	
Assess physical and mental functioning	X	X
Review and complete Advance Directives including: review of previously completed advance care directives, discussion/ completion of POST form, code status, and advance care directives (power of attorney, living will, or advance care plan)	X	X
Name surrogate	X	
Review medical history	X	
Review family history	X	
Review social history (marital status, tobacco use, smoking, alcohol use, drug use, occupation, children) and identify patient's barriers to healthcare access	X	
Dignity and Spirituality assessment (referral to chaplain where applicable)	X	X
Review medications and allergies	X	X
Review symptoms*	X	X
Explain medical condition/diagnosis in lay terms and discuss patient's understanding of prognosis	X	
Discuss questions to ask hepatologist	X	X
Discuss social/family support system	X	X
Develop Care Plan and Goals of Care in the context of the patients current medical condition	X	
Review Care Plan and Goals of Care in the context of the patients current medical condition	X	X
Direct/refer patient towards appropriate resources (e.g. hospice where applicable)	X	X
Record time spent with patient	X	X
Ensure family awareness as applicable	X	X
Communication of Care Plan and pertinent information back to Hepatology MD	X	X

*Symptoms include: lack of energy, lack of appetite, pain, dry mouth, weight loss, drowsiness, shortness of breath, constipation, diarrhea, difficulty sleeping, nausea, vomiting, fever, chills, sweats, sore throat, headaches, change in vision, polyuria, polydipsia, cold/heat intolerance, cough, hemoptysis, chest pain, palpitations, orthopnea, hematuria, renal stones, melena, anorexia, enlarged lymph nodes, bleeding, easy bruising, rhinitis, skin reactions, joint pain/swelling, weakness, myoclonus, sadness, agitation, anxiety, confusion, rash

Outcomes

Primary clinical endpoint:

- Time to first hospital readmission within 1-year post randomization

Secondary outcomes are expected to include:

- Days alive out of hospital within 6-months post randomization
- Total days in hospital within 1-year post randomization
- Total days in ICU within 1-year post randomization
- Number of hospital admissions within 1-year post randomization
- Cost of hospital admissions within 1-year post randomization
- Median length of stay per admission
- Number of transfers to hospice within 1-year post randomization
- Time to hospice
- Liver disease-specific health-related quality of life
- Generic measures of quality of life
- Patient mood
- Patient satisfaction with care
- Caregiver reported stress
- Caregiver reported satisfaction with patient care (including quality of death and dying, as applicable)
- Liver transplant status (deferred, listed, decline)
- MELD score
- Number of completed liver transplants
- Patient diagnoses and physical symptoms (e.g., presence of ascites, variceal bleeding, encephalopathy, delirium)
- Presence of Advance Directives (Goals of Care, Code Status, Surrogate decision-maker, etc.)
- Survival
- Staff satisfaction with intervention procedures

Process outcomes to measure intervention fidelity are expected to include:

- Number of responses to surprise question, number of 'No' responses to surprise question, number of patients with 'No' response to surprise question who are approved for enrollment
- Number of enrolled patients who receive the palliative care intervention
- Use of standardized forms by palliative care providers
- Clear documentation of a plan of care
- Concordance with goals of care (EMR derived, standardized, objective and measurable variables including DNR order non-adherence, aggressive treatment at end of life without expressed patient consent, CPR, mechanical ventilation, intubation, feeding tubes, re-admission, medications, etc.)
- Documented referrals/coordination with social workers or hospice when applicable
- Documented communication of Palliative Care Plan to patient's hepatology provider
- Completed Advance Directive, including designation of a Surrogate Decision Maker

